| Phase | Feasibility pilot study |
| Methodology | Open-label |
| Study Duration | 1 year of accrual. |
| Study Center(s) | Single-center |
| Objectives | 
Primary Objectives
 
 To determine the safety and feasibility of pazopanib given with a low fat meal for therapy of metastatic renal cell carcinoma. 
Secondary Objectives
 
 To determine the overall response rate to pazopanib given with a low fat diet in first-line therapy of metastatic renal cell carcinoma. To explore PK characteristics (Cmax) of pazopanib taken with a low fat meal. |
| Number of Subjects | 16 with interim analysis for safety after 8 subjects have been treated with pazopanib for at least 4 weeks. |
| Inclusion Criteria | 
 Adult (>18 years old) patient with unresectable locally advanced or metastatic RCC with a clear cell component Measurable disease per RECIST 1.1 criteria No prior pazopanib therapy Subject must have ECOG PS of ≤2 Subject must be willing to take pazopanib with a low-fat meal per protocol Subjects are permitted to have had up to 3 prior VEGF or VEGFR targeted therapies, plus any number of prior cytokine therapies (e.g.IL-2) or checkpoint inhibitor therapy (e.g. anti-PD1/PDL1, anti-CTLA4) or mTOR inhibitor therapy(e.g. everolimus, temsirolimus) Platelets > 100,000 mm³, ANC > 1000 mm³ and AST/ALN < 1.5 X ULN; Total Bilirubin < 1.5 times ULN Subject must be willing to discontinue any proton pump inhibitors/strong CYP3A4 inducers or inhibitors (section 9.1) Agree to use effective contraception and stop simvastatin if on it. |

| | |
|---|--|
| 
Exclusion Criteria
 | 
 1. Any concurrent health condition that in the view of the treating physician would pose excessive risk to the subject if he/she is enrolled in the study. 2. Subjects with a history of hemoptysis, cerebral hemorrhage or clinically significant GI hemorrhage or myocardial infarction (MI) within the past 6 months. 3. Patients at significant risk for GI perforation or fistula. 4. Pregnant or nursing mothers. 5. Untreated CNS metastasis. If treated CNS metastasis/es, such treatment must have been completed at least 30 days prior to registration. 6. Subjects with Cirrhosis, HIV, Hepatitis B or C 7. Averaged QTc baseline in 3 ECGs at least 5 minutes apart of ≥ 450 ms. 8. Congestive Heart Failure (NYHA Class III/IV), LVEF $< 50\%$ at baseline. |
| 
Study Product(s), Dose, Route, Regimen
 | 
Pazopanib 400mg (starting dose) PO daily with low-fat meal (LFM) in 14 day cycles. Pazopanib may be increased to 600 mg and subsequently to 800 mg PO with low-fat meal daily starting with second cycle if the prior dose is tolerated. Pazopanib may be decreased to 200 mg PO with low-fat meal daily starting with second cycle if the starting dose is NOT tolerated. Pazopanib dose may be adjusted every 2 weeks based on toxicities. No re-escalation of dose is allowed.
 |
| 
Duration of Administration
 | 
Until progression of disease or unacceptable toxicity or withdrawal from protocol therapy or after 6 cycles (12 weeks) of Pazopanib treatment.
 |
| 
Statistical Methodology
 | 
The feasibility and safety of Pazopanib with low-fat meal will be assessed based on the following statistics with a 95% confidence interval around the reported statistic: frequency of toxicity, severity of toxicities (according to CTCAE version 4.03 criteria), frequency of dose-reductions, duration of therapy, and mean or median total dose taken.
 |

1.0 BACKGROUND AND RATIONALE

1.1 Background

Pazopanib is an orally administered multi-kinase inhibitor targeting VEGFR (vascular endothelial growth factor receptor), PDGFR (platelet derived growth factor) and c-kit, which are critical to growth and proliferation of neoplastic cells. Pazopanib has been FDA approved for advanced renal cell carcinoma (RCC) with a clear cell component. This approval was based on phase 3 clinical trial results in adult patients with measurable, locally advanced, and/or metastatic RCC with either no prior therapy or one prior cytokine therapy randomly assigned 2:1 to receive oral pazopanib (800 mg once daily on an empty stomach) or placebo¹. The primary end point was progression-free survival (PFS). Secondary end points included overall survival, objective tumor response rate (RECIST criteria) and safety. Of the 435 patients enrolled, 233 were treatment naive (54%) and 202 were cytokine pretreated (46%). Progression free survival was significantly prolonged with pazopanib compared with placebo in the overall study population (median, PFS 9.2 v 4.2 months; hazard ratio [HR], 0.46; 95% CI, 0.34 to 0.62; $P < .0001$). In pre-planned subset analyses, pazopanib prolonged PFS in both treatment-naive subpopulation (median PFS 11.1 v 2.8 months; HR, 0.40; 95% CI, 0.27 to 0.60; $P < .0001$), and the cytokine-pretreated subpopulation (median PFS, 7.4 v 4.2 months; HR, 0.54; 95% CI, 0.35 to 0.84; $P < .001$). The objective response rate was 30% with pazopanib compared with 3% with placebo ($P < .001$), with a median duration of response longer than 12 months on pazopanib¹.

In a subsequent non-inferiority trial, pazopanib was compared to sunitinib in therapy of clear cell metastatic renal-cell carcinoma, in 1110 patients who were randomized in a 1:1 manner to receive continuous pazopanib (800 mg once daily on an empty stomach; 557 patients) or sunitinib in 6-week cycles (50 mg once daily for 4 weeks, followed by 2 weeks without treatment; 553 patients)². The primary end point was progression-free survival as assessed by independent review, and the study was powered to show non-inferiority of pazopanib versus sunitinib. Secondary end points included overall survival, safety, and quality of life. Pazopanib was shown to be non-inferior to sunitinib with respect to progression-free survival (hazard ratio for progression of disease or death from any cause, 1.05; 95% confidence interval [CI], 0.90 to 1.22), meeting the predefined non-inferiority margin (upper bound of the 95% confidence interval, <1.25). Overall survival was also similar (hazard ratio for death with pazopanib, 0.91; 95% CI, 0.76 to 1.08). Patients treated with sunitinib, as compared with those treated with pazopanib, had a higher incidence of fatigue (63% vs. 55%), hand-foot syndrome (50% vs. 29%), and thrombocytopenia (78% vs. 41%). Patients treated with pazopanib had a higher incidence of increased levels of alanine aminotransferase (60%, vs. 43% with sunitinib). The mean change from baseline in 11 of 14 health-related quality-of-life domains, particularly those related to fatigue or soreness in the mouth, throat, hands, or feet, during the first 6 months of treatment favored pazopanib ($P < 0.05$ for all 11 comparisons)².

Pazopanib has since become one of the standard first line therapies in metastatic RCC³. If other agents are chosen in the first line setting, pazopanib is often used in subsequent lines of therapy.

Pazopanib Dosing

Conventional Pazopanib dosing WITHOUT FOOD is with an initial dose of 800 mg PO qday, with subsequent dose-reduction to 400mg or 600 mg daily as needed for toxicities. Pazopanib is routinely administered by mouth at least 1 hour before or at least 2 hours after food per the FDA approved package insert. These instructions are primarily to keep absorption of the medication fairly constant from one day to the next. When given as specified in the package insert, absolute bioavailability of the drug is only 21%. It is well known that fat in a meal co-administered with pazopanib results in higher absorption of the drug. Administration of pazopanib with a low or high fat meal has been studied in an

open-label, randomized, crossover, phase I study that evaluated the effect of low- and high-fat meals on the pharmacokinetics (PK) of pazopanib in patients with advanced solid tumors⁴. Pazopanib is highly lipophilic, and therefore high fat meals can either potentiate the absorption of pazopanib, or reduce its solubility by stimulating gastric acid synthesis⁴. Six subjects were enrolled in a lead-in cohort. They received a single dose of pazopanib 400 mg with a high-fat meal and were then monitored for safety for 8 days. Twenty-nine patients were then enrolled in the food-effect cohort and then randomized to receive two single doses of pazopanib 800 mg in either the fed condition (high- or low-fat meal) or fasting condition, in random sequence 14 days apart. After completion of the study, patients were given the opportunity to continue treatment with daily pazopanib 800 mg in the fasting state. Administration of pazopanib with either low- or high-fat meals had resulted in a similar magnitude of increase in the maximum observed plasma concentration (C_{max}) and area under the plasma concentration-time curve (AUC) of approximately twofold as compared with the corresponding values when administered to patients in the fasted condition⁴.

Pharmacokinetic studies have shown that pazopanib doses greater than 800mg daily in the fasting state did not increase systemic exposure of pazopanib at steady state, likely due to saturation of absorption in the gut⁴. Therefore, it is unclear at this time whether the increased C_{max} and AUC of pazopanib when given with food will correlate with higher systemic exposure when these doses are given repeatedly daily with food. Furthermore, although C_{max} and AUC were increased, the half-life of the drug was the same in patients who received pazopanib fasting or with food, indicating that administering pazopanib with food primarily affects its bioavailability⁴. This study did not control for the content and volume of meals the participants ate, and did not perform pharmacokinetic studies on continued dosing of pazopanib with food.

Administration of pazopanib with food in the context of varying day to day diets could indeed result in excessive variability of absorption and systemic levels of the drug. But if pazopanib could be taken with meals of similar fat content daily, higher and fairly consistent absorption of the drug may possibly be achieved safely, potentially translating into equivalent or improved efficacy of pazopanib with smaller quantities of the drug compared to standard administration without food and with an acceptable safety profile.

1.2 Study Rationale

[figure not shown]
- 1) Increased efficacy: Administration of pazopanib with a consistent meal containing a standard low quantity of fat every day could result in higher systemic levels of the drug with low intra-patient variability, translating into higher efficacy against advanced renal cell cancer.
- 2) Lower cost: A similar strategy with abiraterone acetate in castration resistant prostate cancer was recently reported and sets a precedent for our approach⁵. If our approach is shown to be feasible and safe, future strategies could allow intake of similar amounts of the drug to achieve similar or greater efficacy as in the fasting state, resulting in substantial cost savings given its high cost of the medication. For example, abiraterone when taken with food could result in savings of \$3,750 per month per patient at current prices. Assuming patients would only need approximately half the quantity of drug as currently used (given the 2-fold increase in C_{max} and AUC), the potential for cost savings with pazopanib given with low fat diet could be approximately \$3,890 per month per patient at current prices.
- 3) Convenience: Intake of the drug with food also minimizes the practical inconvenience of taking pazopanib in the fasting state.

We hypothesize that administration of pazopanib with low fat meal would be safe and feasible with secondary implications of higher pazopanib levels; potentially translating into greater anti-tumor efficacy in advanced renal cell cancer, with significant cost savings. In the proposed pilot study, we seek to test the feasibility and practicality of this approach and gather preliminary data on adverse effects and the safety profile. We hope to ameliorate any potential for greater toxicities with a dynamic dosing design that incorporates adverse events from each cycle into dosing for the next cycle and a structured symptom specific plan.

1.3 Study Design/Schema

Registered subjects will take pazopanib by mouth with a low-fat meal (**containing less than 400 calories and less than 20% fat or 10 grams per meal**) approximately, some sample meals are described in appendix 1) every day in 14 day cycles, for a total of 6 cycles, with a starting dose of 400 mg and adjusted for the next cycle (dose level +1: 600 mg; dose level +2: 800 mg; dose level -1: 200 mg) based on toxicity assessment during or at the end of each cycle. No dose re-escalations are permitted. Imaging will be performed post 12 weeks of treatment.

An interim analysis for safety will be performed after 8 subjects have completed at least 2 cycles (4 weeks) of therapy.

2.0 STUDY OBJECTIVES

2.1 Primary Objectives

- 2.1.1 To assess the safety and feasibility of pazopanib administered with a low fat meal in therapy of advanced renal cell carcinoma

2.2 Secondary Objectives

- 2.2.1 To estimate the efficacy of pazopanib administered with a low fat meal in therapy of advanced renal cell carcinoma.
- 2.2.2 To explore PK characteristics (Cmax) of pazopanib taken with a low fat meal.

2.3 Endpoints

2.4 Primary Endpoint:

- 2.4.1 To assess the frequency of grade 3 or 4 adverse events associated with pazopanib administered with a low fat meal by CTCAE ver 4.0.

2.5 Secondary endpoints:

- 2.5.1 To estimate the overall response proportion to pazopanib administered with a low fat meal by RECIST 1.1 criteria.
- 2.5.2 To explore Cmax in subjects treated with pazopanib administered with a low fat meal and its potential correlation with toxicity as assessed by CTCAE ver 4.0

3.0 PATIENT ELIGIBILITY

Subjects must meet all of the inclusion and exclusion criteria to be enrolled on the study. Study treatment may not begin until a subject is registered.

3.1 Inclusion Criteria

- 3.1.1 Adult (>18 years of age) with unresectable locally advanced or metastatic renal cell carcinoma with a clear cell component.
- 3.1.2 Subjects must have measurable disease per RECIST 1.1 criteria.
- 3.1.3 Subjects must not have had prior pazopanib therapy.
- 3.1.4 Subjects must have an ECOG PS of < 2.
- 3.1.5 Up to 3 lines of prior VEGF or VEGFR targeted therapy are permitted. Any prior therapy should have been completed ≥ 2 weeks prior to start of study therapy.
- 3.1.6 Subjects may have received any number of the following therapies: cytokine therapy (e.g. high dose interleukin-2) or checkpoint inhibitor therapy (e.g. anti-PD1/PDL1, anti-CTLA4) or mTOR inhibitor therapy (e.g. everolimus, temsirolimus).

3.1.7 Adequate organ and marrow function as defined below:

| | |
|---------------------------|---|
| ANC | > 1000/mm ³ |
| Platelets | > 100,000/mm ³ |
| AST, ALT, Total bilirubin | < 1.5 X ULN. Patients with Gilbert's disease are exempt from this criteria (please see dose-adjustment for Gilbert's as per table 3). |

3.1.8 Subject must be willing and able to take pazopanib with a low-fat meal every day as specified in the protocol.

3.1.9 Subjects must be willing and able to come off any PPI/other strong CYP3A4 inhibitors or inducers/simvastatin.

3.1.10 Ability to understand and the willingness to sign a written informed consent.

3.1.11 All subjects, including those who are surgically sterilized, must be willing to use an effective method of contraception (barrier method of birth control or abstinence) from the time informed consent is signed until 6 months after completion of protocol therapy.

3.2 Exclusion Criteria

3.2.1 Any concurrent health condition that in the view of the treating physician would pose excessive risk to the patient if enrolled in the study.

3.2.2 Subjects with a history of significant hemoptysis per the treating physician's judgment, cerebral hemorrhage or clinically significant GI hemorrhage or myocardial infarction (MI) within the past 6 months.

3.2.3 Patients at significant risk for GI perforation or fistula.

3.2.4 Pregnant or nursing mothers.

3.2.5 Untreated CNS metastasis. If treated CNS metastasis/es, treatment of CNS disease (surgery or radiation) must have been completed at least 30 days prior to registration. Patients could still be on steroids.

3.2.6 Subjects with known history of Cirrhosis, HIV, Hepatitis B or C.

3.2.7 Averaged QTc baseline in 3 ECGs at least 5 minutes apart of ≥ 450 ms.

3.2.8 Congestive Heart Failure (NYHA Class III/IV) or LVEF <50% at baseline.

3.2.9 Uncontrolled hypertension (HTN) despite medical management (Blood pressure (BP) $\geq 160/100$).

4.0 SUBJECT SCREENING AND REGISTRATION PROCEDURES

Subjects will be recruited from the routine clinical practice of the treating oncologists. After informed consent is obtained and PRIOR to the initiation of protocol therapy all patients satisfying the inclusion/exclusion criteria must have eligibility confirmed by the Clinical Trials Office. The patient will not be considered registered and enrolled in the study until all information is confirmed by the Clinical Trials Office Data Manager.

5.0 TREATMENT PLAN

5.1 Treatment Dosage and Administration

Protocol treatment must start within seven business days of registration to the study.

Subjects will take starting dose of pazopanib 400 mg PO once a day with a low-fat meal as specified in the protocol once daily in every 14 days cycles, for a maximum of 12 weeks.

Consecutive doses should be taken approximately 24 hours (\pm 4 hours) apart.

If the subject does not develop significant toxicities as described in Section 5.2 after the first cycle, then the pazopanib dose will be escalated to 600 mg PO once daily with low-fat meal for the next cycle. If the subject does not develop significant toxicities as described in Section 5.2 at 600 mg, then the pazopanib dose will be escalated to 800 mg PO once daily with low-fat meal for the next cycle.

Subject will be assessed for significant toxicities as described in section 5.2 at the end of each cycle by clinical exam and laboratory values including liver function tests. Any grade 3 or 4 pazopanib-related (as assessed by treating investigator) non-hematological toxicities (except specific toxicities listed in table 2, 3 and 4) will necessitate dose reduction by 1 dose level for the next cycle.

No dose re-escalations are permitted.

Table 1 Pazopanib Dose Levels in Study

| Dose Level | Pazopanib with low fat meal |
|------------|-------------------------------------|
| +2 | 800 mg daily |
| +1 | 600 mg daily |
| 0 | 400 mg daily (starting dose) |
| -1 | 200 mg daily |

| ALT/AST >3x ULN with known or suspected Gilbert with mild indirect hyperbilirubinemia (total bilirubin ≤ 6mg/dL and direct bilirubin <35% of total). | Continue pazopanib without dose reduction, but monitor AST/ALT weekly until ALT returns to grade 1 (NCI CTCAE version 4) or baseline. |
| Hypertension | |
| Grade 1: (pre-hypertension with systolic BP 120-139 mmHg or diastolic BP 80-89 mmHg) | None. Blood pressure should be monitored as recommended by the treating physician. |

| | |
|---|---|
| 
Grade 2: Persistent (>24 hours) or recurrent HTN (systolic BP 140-159 mmHg or diastolic BP 90-99 mmHg) or symptomatic BP increase by >20 mmHg diastolic or >140/90 mmHg if previously within normal limits.
 | 
Initiate monotherapy with anti-hypertensive agent of treating physician's choice belonging to the Calcium channel blocker (CCB) or ACE I/ARB class to lower BP back down to goal of systolic less than 140 mmHg and diastolic less than 90 mmHg. Blood pressure should be monitored as recommended by the treating physician and dose adjustment of pazopanib as per judgment of treating physician but is not mandated.
 |
| 
Grade 3: Systolic BP > 160mmHg or diastolic >100mmHg or medical intervention indicated
 | 
Initiate more anti-hypertensive medications or intensive anti-hypertensive therapy with agents of treating physician's choice to bring subject's BP back to goal of systolic < 140 mmHg and diastolic < 90 mmHg. Blood pressure should be monitored as recommended by the treating physician and dose adjustment or discontinuation of pazopanib as per judgment of treating physician.
 |
| 
Grade 4: life-threatening HTN (i.e. malignant HTN or posterior reversible encephalopathy syndrome (PRES))
 | 
Discontinue Pazopanib permanently.
 |
| 
QTc Prolongation
 | |
| 
QTc interval \geq 500msec or > 60msec from baseline QTc interval on averaged 3 ECGs taken at least 5 minutes apart
 | 
Check concurrent medications for causes of QTc prolongation and if considered contributing, discontinue them.
 
Check electrolyte levels in serum including magnesium, potassium and calcium.
 
Continue study drug at 1 dose level lower and recheck ECG x 3 five minutes apart on next visit. If already at -1 dose level, then discontinue pazopanib.
 |
| 
Proteinuria
 | |
| 
Urine Protein Creatinine ratio (UPC ratio) >1 but <3
 | 
Obtain 24 hour urine protein and if <3g, continue at current dose and monitor as clinically indicated.
 |
| 
Urine protein UPC ratio \geq 3 and/or urine protein in 24 hr urine protein \geq 3g/dL/1.73 m²
 | 
Discontinue pazopanib and obtain weekly UPC or 24 urine protein until UPC ratio <3 or 24 hour urine protein is <3g/dL/1.73 m² BSA. Then, can restart pazopanib with a one level dose reduction.
 
If no further dose reductions in pazopanib can be made, then discontinue pazopanib.
 |

| | |
|---|--|
| Nephrotic syndrome | Discontinue pazopanib |
| LV dysfunction or CHF | |
| Grade 1 and 2 | None |
| Decline in LVEF greater $\geq 15\%$ or EF is $< 50\%$. | Stop pazopanib, repeat TTE in 8 weeks and if either of these (decline in LVEF greater $\geq 15\%$ or EF is $< 50\%$) are confirmed, refer to cardiology to institute CHF measures such as beta-blocker, ACEI/ARB etc. |
| Symptomatic heart disease or CHF | Refer to cardiology and discontinue pazopanib permanently if alternative causes are not found. |

Table 4. Management of other specific adverse events.

| Event | Action |
|----------------------------------|---|
| Hemorrhage/bleeding | |
| Grade 1 | None, except if hemoptysis, in which case the PI should be contacted to determine whether continuation of therapy is appropriate. |
| Grade 2 | If non-pulmonary, hold pazopanib until resolves to grade 1 or less. Then can restart pazopanib with a one dose level dose-reduction. If already at (-1 dose level), discontinue pazopanib permanently. If pulmonary, the PI should be contacted to determine whether continuation of therapy is appropriate. |
| Grade 3 or 4 | Discontinue pazopanib permanently |
| Arterial thrombosis | |
| All grades | Discontinue pazopanib permanently |
| GI fistula or perforation | |
| All events | Discontinue pazopanib permanently |

Table 5: Pazopanib dose-adjustments based on other unspecified non-hematological toxicity grade per NCI CTCAE version 4.0.

| NCI CTCAE Grade | Pazopanib |
|-----------------|--|
| 0-2 | No change from original starting dose (except liver toxicity as described in Table 3) |
| 3 -4 | Hold until resolved to \leq Grade 2, then resume with 1 dose level reduction. |

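### Table 3's higher-severity proteinuria row states its 24-hour stop and restart limits as a BSA-scaled concentration (3 g/dL/1.73 m²), in conflict with the plain 3 g limit in the preceding row

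*Combined protocol and SAP*

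**What the plan says.** Section 5.2 sends the reader to Tables 2 to 5 for the dose-adjustment criteria. Table 3 has two proteinuria rows that use a numeric limit, followed by a nephrotic syndrome row that stops the drug.

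- **Lower-severity row.** Entry: "Urine Protein Creatinine ratio (UPC ratio) >1 but <3". Action: "Obtain 24 hour urine protein and if <3g, continue at current dose and monitor as clinically indicated". The limit is a mass.
- **Higher-severity row.** Entry: "Urine protein UPC ratio \geq 3 and/or urine protein in 24 hr urine protein \geq 3g/dL/1.73 m²". Action: "Discontinue pazopanib and obtain weekly UPC or 24 urine protein", and this continues "until UPC ratio <3 or 24 hour urine protein is <3g/dL/1.73 m² BSA. Then, can restart pazopanib with a one level dose reduction". The limit is printed in g/dL/1.73 m² both for stopping and for restarting.

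Two general rules sit around these rows. Section 5.1 says that grade 3 or 4 drug-related "non-hematological toxicities (except specific toxicities listed in table 2, 3 and 4) will necessitate dose reduction by 1 dose level for the next cycle". Table 5 is titled "Pazopanib dose-adjustments based on other unspecified non-hematological toxicity grade per NCI CTCAE version 4.0". Nothing else in the protocol defines or corrects the proteinuria unit.

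**The concern.** The two rows are meant to meet at one boundary. The lower row orders a 24-hour collection so that a patient with an intermediate UPC can be sorted into continue or stop. That works only if both rows measure the collection in the same unit, and they do not.

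Three things follow if the higher row is applied as printed:

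- Its 24-hour stop limb is practically out of reach.
- A patient with UPC between 1 and 3 and a 24-hour protein of 3 g or more fails the lower row's condition for continuing, but no action is stated, because the stop limit is not met.
- The restart conditions are joined by 'or', and weekly monitoring may use either test. Almost any 24-hour result would therefore release a held patient, even with UPC still at 3 or more.

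At stake is consistent handling of a stop/restart decision in a trial whose primary objective is safety and feasibility. Dose reductions, treatment duration and total dose are among the outcomes that Section 11.1 will describe.

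**Working it through.** **Inputs from the protocol.** Lower row: 3 g per 24-hour collection. Higher row: 3 g/dL/1.73 m², for stop and restart. Stop combines UPC and the 24-hour result by 'and/or'; restart combines them by 'or'.

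**Assumptions, not in the documents.** Urine volume of 1-2 L per day (0.5-3 L as a wider check) and BSA of 1.5-2.2 m². A concentration scaled by BSA has no clear meaning, so the literal reading is worked at BSA 1.73 m², where the scaling drops out.

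**Step 1: literal limit as a daily mass.** Daily mass (g) = concentration (g/dL) × 10 × volume (L).
- 1 L: 3 × 10 × 1 = 30 g; 30/3 = 10 times the lower row's limit.
- 2 L: 3 × 10 × 2 = 60 g; 60/3 = 20 times.
- Wider check: 0.5 L gives 15 g (5 times) and 3 L gives 90 g (30 times).

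In the other direction, 3 g per day in 1-2 L is only 0.30-0.15 g/dL. No volume in the range reconciles the two rows.

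**Step 2: the BSA-indexed reading.** Absolute limit = 3 × BSA/1.73.
- 1.5 m²: 3 × 1.5/1.73 = 2.60 g.
- 2.2 m²: 3 × 2.2/1.73 = 3.82 g.

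**Step 3: two illustrative patients, each with 1.5 L (15 dL) of urine.** Patient A has UPC 2 and 4 g: 4/15 = 0.27 g/dL, about 11 times below the printed limit. Patient B is on hold with UPC still 3 or more and 6 g: 6/15 = 0.40 g/dL.

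| 24-hour limit read as | Patient A | Patient B |
|---|---|---|
| 3 g/dL (literal) | Fails the condition for continuing; stop limit not met; no stated action | Restart permitted |
| 3 g per 24 h | Stop (4 ≥ 3) | Stays on hold (6 ≥ 3) |
| 3 g/24 h/1.73 m² (2.60-3.82 g) | Stop (4 > 3.82) | Stays on hold (6 > 3.82) |

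**Step 4: do the general rules supply patient A's action?** Not clearly. Section 5.1 excepts toxicities listed in Table 3, and Table 5 is for toxicities not specified elsewhere. Both also work by CTCAE grade, which the proteinuria rows do not state.

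**Step 5: how often is the row reached?** Sections 6.2.13, 6.3.3 and 6.4 schedule UPC at screening and at the end-of-treatment visit only. The Day 1 list for each cycle (Section 6.3.1) has no urine protein test. End of treatment falls at the end of cycle 6 (± 7 days), and 12 weeks is the maximum treatment. For a patient who completes therapy, the first scheduled on-study UPC therefore comes at about the time dosing ends. During dosing, the row comes into play only after unscheduled urine testing or because of a high screening value. The latter is possible because Section 3 sets no proteinuria limit for entry.

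**The case against.** The strongest reply is that nobody would apply the unit literally. Both cells name a 24-hour urine protein, the adjacent row gives 3 g for that test, and the literal limit works out at tens of grams per day. This largely stands: a clinician would probably infer 3 g. It does not settle the matter, because the printed reference to 1.73 m² BSA also suggests indexing, and the protocol does not say which was meant.

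Second, the row will seldom be used, given the UPC schedule. This stands and limits the importance of the point. It does not remove it, since the row itself calls for weekly testing once a patient is held.

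Third, other protections remain: UPC of 3 or more alone still stops the drug, nephrotic syndrome stops it, restart is one level lower, and a continuous hold of 4 weeks or longer removes the patient. All of these are unaffected by the unit.

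Fourth, Table 3 is labelled as giving examples, so the general grade 3-4 rules might be thought to fill any gap. The label weakens the case that those rules are closed off, but Section 5.2 treats the table as the dose-adjustment criteria, and the label does not supply the missing action.

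A reader might also infer that patient A falls under neither proteinuria row. The documents do not support that. UPC 2 places the patient in the lower-severity row, and 4 g fails its condition for continuing, so unchanged dosing is not authorised. What is missing is the next step.

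**Conclusion.** The point holds as a minor correction to a safety rule. The unit is wrong for the test it governs, it appears in both the stop and restart cells, and it conflicts with the preceding row. The appearance in two cells, once followed by 'BSA', makes a text-extraction fault unlikely.

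The practical size is the gap between 3 g and about 2.6-3.8 g per 24 hours, on the assumed BSA range. The 10- to 20-fold discrepancy describes only the literal reading at an assumed 1-2 L of urine. A reader might infer from it that patients would in practice be dosed through 30-60 g per day. The documents do not support that, given the adjacent 3 g limit and the intact UPC stop limb. The literal restart wording nevertheless permits restart with UPC still at 3 or more, which is reason enough to correct it.

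Sample size, the interim rule and the planned confidence intervals are unaffected. Confidence in the unit error is high. Which unit was intended cannot be determined from the documents.

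**What to change.** In the higher-severity proteinuria row of Table 3, replace the g/dL/1.73 m² limit with 3 g per 24 hours in both the stop and the restart cell. The two rows then share one boundary: below 3 g continue, at or above 3 g stop, and restart one level lower once below 3 g. If the sponsor confirms that BSA indexing was intended, print 3 g/24 h/1.73 m² in both rows instead.

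The change leaves the restart 'or' as it is, so either test alone can still permit restart, including UPC below 3. Adding UPC tests during treatment would be a separate monitoring choice and is not needed here.

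The cost is wording in two table cells, or three if the indexed unit is carried to the preceding row. No new test, visit or patient is required.
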